STATISTICAL ANALYSIS PLAN (SAP)

A Cluster-Randomized Trial of the Northwestern Embedded Emergency Department Physical Therapy (NEED-PT) Protocol for Acute Low Back Pain

February 20th, 2025

Version 2.0

NU IRB: STU00213134

Registration: NCT04921449

Statistical Analysis Plan (SAP) Revision History

Version Number: 1.0

Version Date: 10/04/2021

Summary of Revisions Made: Original Version

Version Number: 2.0

Version Date: 2/20/25

Summary of Revisions Made:

- Context for changes: The final NEED-PT trial participant was enrolled on 7/11/24 and we anticipate final data collection on 7/25/25 (two-week follow-up window for the 12-month follow-up timepoint). We are modifying the SAP in advance of our anticipated database lock on 7/25/25.
- Expanded the methodology of Exploratory Analysis #4. As primary treatment classification is available only among those participants in the treatment arm (NEED-PT), we must specify our process for matching participants in the control arm (usual care) to comparable treatment classifications.
- Additional detail has been added to Sensitivity Analyses #1-#3. We anticipate that the total number of participants meeting criteria for Sensitivity Analysis 1 and 2 may be low and have therefore specified combining these analyses should $n \leq 10$ in either case. We also clarify that Sensitivity Analysis 3 (per-protocol) is the same analysis previously described as a “complier analysis.”
- We now specify our approach to missing data, which we piloted in a similarly structured trial of an ED physical therapy intervention for dizziness (PMID 39951266).

STATISTICAL ANALYSIS PLAN (SAP)

A Cluster-Randomized Trial of the Northwestern Embedded Emergency Department Physical Therapy (NEED-PT) Protocol for Acute Low Back Pain

Principal Investigator: [name] MS

Statistical Team: [name]; [name], [name], MS

1. INTRODUCTION

This document outlines the proposed analyses for the NEED-PT study. Briefly, NEED-PT is a physician-randomized (i.e., physicians serve as clustering or randomization units) trial evaluating efficacy of an embedded emergency department (ED) physical therapist in comparison to usual care. Individual ED patients will be consented and enrolled during their index ED visit and will follow the randomization assignment of their treating physicians. The primary outcome data will be analyzed at three months after the index ED visit, with additional data collection up to 12 months for evaluation of longer-term effects and exploratory endpoints.

Study Aims

The overarching study aims are as follows. **This SAP will focus on the details for Aim 2 analyses, which will guide the reporting of the primary study findings.** We reserve details of analyses surrounding additional aims for separate document(s):

Aim 1: Develop and field-test the Northwestern “Embedded” ED Physical Therapy (NEED-PT) intervention protocol for the routine co-evaluation of all ED patients with acute low back pain.

We will co-locate the ED physical therapist with the ED physician as part of the primary treatment team in order to remove biases in treatment selection and allow for earlier integration of ED-PT into patient care. A formalized protocol will enhance intervention fidelity in Aim 2 and facilitate dissemination of our care model.

Aim 2: Conduct a single-center, physician-randomized trial (n=40) comparing NEED-PT to usual care among ED patients (n=360) with acute low back pain to evaluate a primary outcome of pain-related functioning at three months and a secondary outcome of opioid use at three months.

H1: Patients receiving NEED-PT will report greater improvement in pain-related functioning compared to patients receiving usual care, as measured by average PROMIS Pain-Interference score

H2: Patients receiving NEED-PT will use fewer daily opioids on average.

Aim 3: Compare rates of diagnostic imaging utilization for ED visits with low back pain among ED physicians randomized to NEED-PT versus usual care.

H1: ED physicians randomized to NEED-PT will have a lower rate of diagnostic imaging utilization for low back pain compared to ED physicians randomized to usual care.

For patients enrolled in the study, study time points include baseline assessment (completed at the index ED visit), Week 1, Month 1, Month 2, Month 3 (primary endpoint), Month 6, and Month 12.

2. STUDY OUTCOMES

Primary Outcome

The primary efficacy outcome is **PROMIS-Pain Interference Score (PROMIS-PI)** three months after the index ED visit. PROMIS-PI measures the self-reported consequences of pain on relevant aspects of a person's life, including social, cognitive, emotional, physical, and recreational activities. We will use the computer-adaptive format to minimize respondent burden. Scores are standardized to the general U.S. population, with a score of 50 representing the population mean and a standard deviation of 10 points. The time frame of interest for the PROMIS-PI is "in the past 7 days," meaning that participants provide responses based on their symptoms over the last week. The minimum clinically important difference for low back pain is in the range of 3.5-5.5 points. We will treat this variable as continuous in analyses.

Secondary Outcomes

Secondary efficacy outcomes include:

- 1) **Oswestry Disability Index (ODI)** at three months. *ODI* is a disease-specific instrument that contains 10 questions relating to low back pain intensity, personal care, lifting, walking, sitting, standing, sleeping, social life, traveling, and employment/homemaking. The ODI score ranges from zero (no disability) to 100 (maximum disability), with an estimated minimum clinically important difference of six points for acute low back pain. The time frame of interest for the ODI is “today,” meaning that participants provide responses based on their current symptoms on the day of survey response. The modified ODI replaces an item from the original ODI pertaining to sex life with a new item pertaining to employment/homemaking. We expect this outcome to be largely correlated with PROMIS-Pain Interference. We will treat this variable as continuous in analyses.
- 2) **Patient-Reported Opioid Use** at three months. This will be collected using a customized instrument assessing whether participants have taken any opioid medication in the last 24 hours. The 24-hour timeframe was selected to maximize accuracy in patient recall and has been used previously. In brief, opioid medications are listed by brand and generic names; a “yes” response to any medication triggers an additional query asking the participant to specify the medication dose (e.g., oxycodone 10mg) and quantity (e.g., four pills), allowing for standardization by morphine milligram equivalents (MME). We anticipate treating this variable as either count or a binary (any dose vs. none), or continuous (MME) for analyses.

Exploratory Outcomes

We expect the following outcomes to be related to the primary and the major secondary outcomes of interest. We deem the more exploratory in nature, and they thus carry less weight in analyses and overall inferences regarding efficacy of intervention.

- 1) **Opioid Prescription Filling** will be queried in the state prescription monitoring database. We anticipate treating this variable as count, binary, or continuous (MME).
- 2) **Patient-Reported Prescription Analgesic Use** in the last 24 hours will be collected using the same customized instrument described above for opioid use. Prescription analgesics include: opioids, benzodiazepines, skeletal muscle relaxants, and gabapentinoids. We anticipate treating this variable as either count or binary.
- 3) **Prescription Analgesic Filling** will be queried in the state prescription monitoring database. Prescription analgesics include: opioids, benzodiazepines, skeletal muscle relaxants, and gabapentinoids. We anticipate treating this variable as either count or binary.
- 4) **Numeric Pain Rating Scale (NPRS)** measures pain intensity from 0 to 10 and is easily understood by laypersons, clinicians, and researchers. We will assess a single item relating to average pain intensity over the last 24 hours. We plan to treat this as a continuous outcome, but we anticipate requiring transformation or nonparametric analyses, as this variable will likely be skewed and exhibit flooring / ceiling effects.
- 5) **Global Rating of Change (GROC)** is a single-item survey widely used by clinicians and researchers to quantify functional disability in low back pain and evaluate the overall effectiveness of therapy. This item ranges from zero (a very great deal worse) to 14 (a very great deal better). We plan to initially treat this measure as continuous, but we anticipate exploring this outcome as a count variable, requiring transformation, or using nonparametric analyses.
- 6) **Pain Catastrophizing Scale (PCS-4)**. The original PCS is a 13-item survey measuring the degree to which an individual catastrophizes in response to pain. PCS scores correlate closely with pain intensity and disability over time; higher PCS scores are associated with progression from acute to chronic pain. We will utilize the brief 4-item PCS measure containing original items 3, 6, 8, and 11 to reduce respondent burden. We will treat this variable as continuous in analyses.
- 7) **Pain Self-Efficacy Questionnaire (PSEQ-4)**. The original PSEQ is a 10-item survey measuring the confidence with which individuals can do things despite pain. We will utilize the brief 4-item PSEQ measure containing original items 4, 6, 8, and 9 to reduce respondent burden. We will treat this variable as continuous in analyses.
- 8) **Advanced Healthcare Resource Utilization**. We will assess the proportion of participants who utilized advanced healthcare resources for low back pain after their index ED visit, defined as advanced imaging (e.g., magnetic resonance imaging) or procedures/surgery (e.g., epidural steroid injection, lumbar discectomy).

- 9) **ED Diagnostic Imaging Utilization.** We will assess the proportion of ED visits in which diagnostic imaging of the lower back was performed, including plain radiography, computed tomography, and magnetic resonance imaging.
- 10) **Additional outcomes (not discussed in detail in this SAP) that are a part of the third study aim include:** ED length of stay, ED disposition (admit, observation, discharge), total costs/charges.

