6. STATISTICAL METHODS

We plan to use descriptive statistics to summarize baseline patient and physician-level variables both overall and by arm. We will use mean±standard deviation (or median and interquartile range [IQR] as appropriate) for continuous variables and frequency / percentage for categorical variables. Specifically, we will summarize age, sex, Keele STarT score, baseline patient-reported outcome scores (PROMIS-PI and ODI), analgesic medication prescription at ED discharge, and the variables listed above. Analyses will involve normal theory methods in general, and in cases of violations of assumptions, we will consider transformation and / or nonparametric / exact methods as appropriate.

Analyses will assume a two-sided 5% significance level. All primary efficacy and safety analyses will be pre-specified as outlined in this SAP, and deviations from planned analyses or post hoc analyses will be labeled as such in any reports or dissemination materials. We do not plan to control for multiple hypothesis tests.

In analyses for each outcome, we plan to control for the respective outcome value at baseline (i.e., in an analysis of covariance [ANCOVA] approach). Analyses for the primary outcome (Y) will involve a linear mixed model (LMM) with repeated measures with fixed effects for: study arm, baseline outcome score (Y0), timepoint, timepoint-by-arm interaction, and known influential predictor effects (age, sex, Keele STarT score). Inference will focus on treatment impacts for the outcome at three months. We will include a random physician effect to account for both within and between physician variability and also to allow for estimation of the intra-cluster correlation coefficient (ICC). The repeated measures on the same participant over time will also introduce a correlation structure across time points, providing the justification for modeling the correlation structure at the

participant level over time. We will use an unstructured correlation matrix to account for the repeated measures within a participant as this has the least assumptions. If the model does not converge or parameters cannot be estimated under this unstructured covariance pattern, we will explore simpler covariance patterns using residual estimated maximum likelihood (REML) comparisons. Including repeated measures per participant will allow us to make most use of all participant data after baseline. We will use assume an unstructured covariance across time.

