To evaluate efficacy, the Wald model type III test for fixed arm effect will be evaluated assuming a two-sided 5% type I error rate. The primary contrast of interest to address the primary research aims involves the comparison of the model-estimated mean outcome score at three months (T4) across study arms. This modeling strategy is robust to unbalanced (i.e., incomplete) data across study time points. We will also provide results for unadjusted analyses (i.e., without accounting for the pre-specified covariates). Analyses of additional outcomes will follow the same general analytic strategy: LMM with fixed arm, baseline outcome value, influential baseline covariate effects, and a random physician effect and covariance patterns to account for repeated measures within participants. We chose to incorporate baseline outcome as a covariate in the model, rather than as a time point, based on clinical reasoning. As these baseline values (e.g., PROMIS-PI score at the index ED visit) are assessed pre-intervention and primary analyses aim to assess outcome(s) as follow-up accounting for pre-intervention state. Incorporating this baseline value in the analytic model as a fixed effect will increase precision and reduce bias on the intervention effect estimate for primary outcome at the time point of interest as the baseline value will likely be highly correlated with outcome at follow-up (previous data: $p < 0.001$ for both PROMIS and ODI).

Residual diagnostics will assess model fit and assumptions, and in the case of violation, we will explore transformations / nonparametric methods as indicated above. In the event of poor model fit, we may explore different distributional assumptions as appropriate (e.g., Poisson for count or rate data) with the corresponding canonical link (e.g., log) function. As above, we will assess model fit via residual diagnostics and may consider transforming or nonparametric methods as needed.

Analyses for outcomes that are either binary or count will follow the same general approach as above; however, they will involve generalized linear mixed effects (GLMMs) models with the appropriate distributional (e.g., binomial or Poisson) and link (e.g., logit or log) assumptions. Modeling the covariance structure for these outcomes may result in unstable model estimates. If this occurs, we anticipate removing the random physician effect and including a random participant effect instead to account for correlation.

Exploratory Analyses

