In addition to repeating the above analyses with exploratory outcomes, we will conduct exploratory analyses to study effects among subgroups of patients (moderator analyses) and examine the potential impact of PT use among patients in the control arm.

Planned moderator analyses will include the following moderators:

1. Opioid naivete as measured by whether patients report taking opioids within the last 24 hours at their index ED visit or have a history of opioid prescription filling in the Illinois prescription monitoring program within the last 3 months.
2. Initial symptom burden measured as “moderate/severe” if their baseline measures of PROMIS pain scores are ≥ 60 or their STarT score registers as “high risk,” defined as a subscore ≥ 4 (questions 5-9).
3. Age ≥ 65 years old
4. Primary treatment classification, as per the clinical care protocol (directional preference, traction, stabilization, manipulation, nociplastic presentation). As primary treatment classification is assigned only in those participants in the treatment arm (NEED-PT), we will use two approaches to study the effects of treatment classification. First, we will modify GLMM to include treatment classification effects (as opposed to just a study arm effect). Second, we will use matching methods (e.g., propensity score matching or augmented synthetic controls) to match individuals in the NEED-PT arm who have a given primary treatment classification to control arm participants on baseline covariates. We would then use GLMM to estimate the impact of each treatment classification separately.

Analyses will focus on PROMIS-PI scores measured three months after patients’ index visits, as well as ODI scores and opioid use (proportion using an opioid within the last 24 hours) at the same time point. Analyses will involve generalized linear models with appropriate link functions (identity for PROMIS-PI and logit for opioid

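### The three-month opioid outcome has three permitted forms and no main one, so its two-sided 5% level is not guaranteed

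*SAP*

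**What the plan says.** SAP Section 1 names opioid use at three months as the secondary outcome of Aim 2 and attaches a hypothesis to it: "Patients receiving NEED-PT will use fewer daily opioids on average". Section 2 describes the instrument. It first asks whether any opioid was taken in the last 24 hours, then asks dose and quantity for each medication reported. On the form to be analysed, Section 2 says: "We anticipate treating this variable as either count or a binary (any dose vs. none), or continuous (MME) for analyses". By contrast, PROMIS-PI and ODI are each fixed as continuous.

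Section 6 sets the level ("Analyses will assume a two-sided 5% significance level") and declines adjustment ("We do not plan to control for multiple hypothesis tests"). Binary and count outcomes get generalized linear mixed models "with the appropriate distributional (e.g., binomial or Poisson) and link (e.g., logit or log) assumptions". Residual diagnostics may lead to other distributions, transformations or nonparametric methods. If the covariance modelling is unstable, the physician effect is expected to give way to a participant effect. One form is fixed only in the exploratory moderator models, which take "opioid use (proportion using an opioid within the last 24 hours" and a logit link.

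The revision history dates Version 2.0 to 2/20/25, after the last enrolment on 7/11/24 and before the anticipated lock on 7/25/25. It revises other analyses and leaves the opioid form open.

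**The concern.** The three forms answer different questions. An intervention can reduce the amount taken by continuing users without changing the share who use, and the reverse. If the form is chosen once results by arm are available, whichever of the three favours the intervention can be reported as the planned opioid result. The rule in Section 6 that deviations and post hoc analyses are labelled does not catch this, because picking a listed form is not a deviation. A headline Aim 2 claim would then carry a nominal 5% level that the plan does not secure.

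A second, conditional risk lies in the count form. Poisson is the only count distribution the SAP names, and a 24-hour pill count that is zero for most people and several for users varies more than a Poisson model allows.

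**Working it through.** **The plan's own figure.** Section 8 gives no figure for the opioid outcome. Its worked figure is 84% power for PROMIS-PI, with 16 physicians per arm, m = 7 participants each (112 per arm), a 3.5-point difference, SD 10, ICC 0.10 and baseline correlation 0.50. Taking a cluster autocorrelation of 1 (my assumption):

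- Design effect = 1 + (7 − 1) × 0.10 = 1.6.
- r = [7 × 0.10 + 0.90 × 0.50] / 1.6 = 0.719, so 1 − r² = 0.483.
- Variance = (2 × 100 / 112) × 1.6 × 0.483 = 1.381; SE = 1.175.
- Power = Φ(3.5 / 1.175 − 1.96) = Φ(1.018) = 84.6%, against 84% stated.

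The figure reproduces, so the same layout (32 physicians × 7 = 224) is used below.

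**Bounds for a choice among three tests at 5%.** If independent: 1 − 0.95³ = 14.3%. Bonferroni sum: 3 × 0.05 = 15%. The three forms share the same users and are strongly correlated, so the true rate lies lower and has to be simulated.

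**Assumptions, none in the SAP.** Use at three months of 5, 10 or 20% (224 × 0.05, 0.10, 0.20 = about 11, 22, 45 users). Mean count among users of 1.1 (number of opioids), 2 or 4 (pills). Physician SD on the logit scale of 0 or 0.6. 5, 7.5 or 15 MME per unit.

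**Free choice under no effect.** Each form was tested by a physician-level t-test; 4,000 runs per row, Monte Carlo error about 0.4 points on the last column.

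| Use | Mean count in users | Physician SD | Binary | Count | MME | Any of three |
|---|---|---|---|---|---|---|
| 5% | 4 | 0 | 4.7% | 4.3% | 4.1% | 7.5% |
| 10% | 1.1 | 0 | 4.8% | 5.1% | 4.5% | 7.6% |
| 10% | 2 | 0 | 6.2% | 5.8% | 4.9% | 9.3% |
| 10% | 4 | 0 | 4.6% | 4.4% | 4.0% | 8.0% |
| 20% | 2 | 0 | 4.8% | 5.1% | 4.8% | 9.0% |
| 20% | 4 | 0 | 5.4% | 5.3% | 5.2% | 9.5% |
| 20% | 4 | 0.6 | 5.5% | 4.9% | 4.6% | 9.0% |

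At 5% use with mean counts of 1.1 or 2, runs of about 1,000 gave 5.0 to 7.5%. The 5.0% came from the sparsest setting, where each single test rejected only about 3% of the time.

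**Why the meaning of *count* matters for Poisson.** With a share p using, and mean m and variance s² among users, variance/mean = (s² + m²)/m − p·m; Poisson assumes 1. Take p = 0.10:

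- Number of opioids (m = 1.1, s² = 0.09): 1.30/1.1 − 0.11 = 1.07.
- Pills, m = 2 (1 plus a negative binomial of mean 1, size 2; s² = 1.5): 5.5/2 − 0.2 = 2.55.
- Pills, m = 4 (negative binomial mean 3, size 2; s² = 7.5): 23.5/4 − 0.4 = 5.5.

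**Simulated error of the Poisson mixed models under no effect.**

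| Mean count in users | Physician effect, likelihood ratio | Physician effect, Wald | Participant effect only (fallback) |
|---|---|---|---|
| 1.1 | about 5–6% | about 2–5% | 3% |
| 2 | about 5–8% | about 5–14% | 13–22% |
| 4 | about 16–25% | about 23–45% | 41–51% |

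These rest on 300 to 1,000 runs per setting and are approximate; the likelihood-ratio column is safer than the Wald column. The fallback runs used six follow-ups, the month-3 contrast and an assumed participant SD of 2.0 on the logit scale (one setting used the physician SD of 0.6 as well).

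**The case against.** Several stronger readings are tempting, and the SAP does not support them.

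- *The plan runs three tests and reports the best.* The wording is either/or and anticipates one treatment of the variable. If one form were fixed before results by arm are seen and tested validly, 5% would hold. The simulated rates describe what the plan permits, not what it commits to.
- *The team could already have chosen on results.* Nothing says so. Section 10 limits interim summaries to aggregate figures not split by arm and bars formal analysis before lock. Completed month-3 follow-up is not unblinded data.
- *Declining multiplicity control is the fault.* Across different secondary outcomes that is an open, defensible choice. The fault is several candidate tests of one outcome.
- *Poisson is prescribed and breaks the test.* It is only an example, with diagnostics behind it, and the inflation vanishes if *count* means number of opioids. A plain Poisson test without random effects, at an assumed average of three pills per user, rejects about 25 to 30% of the time, but that is not the SAP's model.
- *The SAP contradicts itself.* H2 is a hypothesis in plain words, and the moderator models use one of the permitted forms. They point different ways without being incompatible.

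It is also fair to say that H2 concerns quantity, so MME could be named as the main form, and that about 22 users at 10% use is sparse for a logistic mixed model.

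What stands after all this: none of these safeguards selects a form, and all three forms remain within plan.

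**Conclusion.** The point holds as a gap in specification. The secondary opioid outcome has no main form or effect measure, *count* is undefined, and the stated two-sided 5% level is therefore not guaranteed. Free choice among three valid tests gives roughly 6 to 10%, against about 4 to 6% for each test alone in most settings. That is a rise of a few points on one secondary outcome, and it rests on the assumed 5 to 20% use and on the assumed counts.

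The Poisson risk is conditional: little or none for a number of opioids, moderate at two pills per user, large at four, and greater if the physician effect is dropped. The primary outcome is not affected. The change should be made before lock, but it does not threaten the trial's main conclusion.

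**What to change.** In an SAP revision before database lock:

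1. Name any opioid use in the last 24 hours at three months (yes/no) as the single secondary opioid analysis, by a logistic mixed model that keeps the physician effect, and state its effect measure. This matches the instrument's opening question and the moderator models.
2. Leave H2 as worded. Rewording a hypothesis after month-3 data exist would invite the criticism this change is meant to remove. Label MME and any count as supportive analyses of quantity.
3. Define *count*. If it means pills, replace Poisson with a model that allows overdispersion and excess zeros.
4. Because events may be sparse, name a fallback that still respects physician clustering, for example a comparison of physician-level proportions, instead of dropping the physician effect for this outcome.

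The cost is a few sentences of SAP text. The binary form is less sensitive to dose reduction among continuing users and does not itself measure the quantity in H2; the supportive MME analysis shows that, without a claim at the 5% level.
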